The University of Washington is the sponsor of the study which is supported by an anonymous funder who does not have any ownership over the management and conduct of the study, the data, or the rights to publish.

III. Objectives

The objective of the study is to measure the proportion of individuals who are initiated on antiviral therapy within 48 hours of symptom onset using a home-based self-test, followed by a telehealth consultation to diagnose influenza and home delivery of antivirals

Primary Outcome Measures

The primary outcome measure will be the proportion of eligible individuals who initiate antiviral therapy at home within 48 hours of symptom onset utilizing a home-based test and the telehealth app for influenza diagnosis and rapid home-delivery of antivirals. It will be calculated using binomial regression with log link, where the number of drug eligible influenza-diagnosed individuals, defined as the number of individuals eligible to receive BXM with both self-test positive influenza and laboratory-confirmed influenza, reporting administration of the study drug within 48 hours of symptom onset is divided by the total number of drug eligible individuals with both self-test positive influenza and laboratory-confirmed influenza.

Secondary endpoints:

- Proportion of individuals who test positive for influenza using the home-based test within 48 hours of symptom onset
- Proportion of individuals with a positive home-based influenza self-test who have a positive test confirmed by the central laboratory
- Sensitivity and specificity of a self-test compared to a laboratory-based molecular influenza test
- Proportion of individuals who are delivered antivirals within 48 hours of symptom onset
- Proportion of individuals who self-report administration antiviral therapy within 48 hours of symptom onset
- Symptom duration and severity among drug eligible and drug ineligible influenza-positive individuals
- Proportion of families with influenza infection diagnosed within 7 days of an index case (another influenza-positive household member)
- Viral quantity and duration of viral RNA detection among drug eligible and drug ineligible influenza-positive participants
- Proportion of drug ineligible study participants seeking medical care for respiratory illness symptoms
- Proportion of individuals who choose to take a self-test among those who are eligible to take a self-test

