- Within-host variation in influenza strains between the first and the third viral swab
- Cost effectiveness, assessed using health resource utilization (visit to clinic, hospital, pharmacy, emergency department) and school and work absenteeism
- Proportion with antiviral resistance, assessed by genetic sequencing of influenza strains from the drug eligible and drug ineligible study participants

Hypothesis

Primary hypothesis:

- A home-based approach to influenza infection control will result in a large percentage of drug eligible individuals diagnosed with influenza initiating antiviral therapy within 48 hours of symptom onset.

Secondary hypotheses:

- Home-based approach to influenza infection control and rapid delivery of antiviral therapy will decrease symptom severity in the drug eligible individuals diagnosed with influenza that administer antiviral therapy within 48 hours of symptom onset compared to drug eligible, influenza-infected individuals that administer antiviral therapy greater than 48 hours after symptom onset.
- Home-based approach to influenza infection control and rapid delivery of antiviral therapy will decrease the duration of viral RNA detection in the drug eligible, influenza-infected individuals that administer antiviral therapy within 48 hours of symptom onset compared to drug eligible, influenza-infected individuals that administer antiviral therapy greater than 48 hours after symptom onset.

IV. Study Population

The study will be conducted in households with at least 3 members, where at least 2 of these members must be eligible to receive BXM, in the Seattle area. Participants aged 12 years or older, weighing at least 40 kg, will be drug eligible. Participants of any age that reside in the same household as the case at least 4 days per calendar week will be drug ineligible study participants. Drug eligible study participants will receive baloxavir intervention when appropriate,

and all drug eligible and drug ineligible participants will receive a 7-day follow-up from the study team per illness episode.

Study size

The study is being conducted in the Seattle, WA area over one influenza season. The goal is to enroll 250 households, with enrollment occurring prior to and during the annual influenza season.

Household enrollment criteria

The household must meet all the following enrollment criteria:

Household inclusion criteria

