Person-to-person transmission: We will use the CDC definition for influenza transmission that refers to the ability of an influenza virus to spread from one person to another, most commonly through large or small droplets containing influenza virus that are expelled when a sick person is coughing or sneezing.

XI. Statistical Analyses

The primary objective is to precisely estimate the proportion of drug eligible individuals with an influenza diagnosis who initiate treatment within 48 hours. We define precision in terms of the width of a 95% confidence interval. The width of a 95% CI will be less than or equal to $\pm 1.96 \cdot 0.5/\sqrt{n}$ where n is the number of individuals who test positive for flu. With 250 households participating and an attack rate of 25% we expect 63 individuals with confirmed influenza infection. This will give a 95% CI for the proportion initiating treatment of ± 0.12 or less.

The proportion of drug eligible individuals receiving the drug and initiating treatment within 48 hours of symptom onset using home-based self-test and delivery methods will be estimated. Binomial regression with log link will be used to calculate the relative risk of receiving and initiating treatment within 48 hours by demographic and clinical factors, including age, sex, race/ethnicity, symptom types, symptom severity, and duration of symptoms. The RR, 95% confidence intervals and p-values will be reported.

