A list of serious adverse events will be presented by shelter and by treatment v. intervention period. As defined in the study protocol, serious adverse events include death, a life-threatening reaction to the study drug (or placebo) or other study procedure, hospitalization, or significant or persistent disability or impairment. The incidence of SAE's (events/person-days of follow-up) will be presented both (1) overall and (2) by case v. non-cases. We will test for a difference in SAE rate between the two study periods (intervention v. control) using an exact Poisson test in R.

Baloxavir-resistant influenza transmission

Evidence of a strong intervention effect causing incidence of baloxavir-resistant influenza strains will be evaluated using linear mixed effects logistic regression. The unit of analysis will be influenza-positive tests, and the outcome will be binary: baloxavir-resistant or not baloxavir-resistant.

B5. Power sample size

Table 1. Sample size calculations: Number of clusters needed per arm for two-group cluster-randomized trial - Household intervention study

Effect size (% reduction in flu incidence)			
Power	0.30	0.40	0.50
0.80	57	84	129
0.90	76	112	172

All calculations above assume an ICC of 0.29, anticipated average (or actual) cluster size of 4, and a 15% transmission rate for flu.

Based on these calculations, an arm size of 250 households should be sufficient to detect a 30% reduction in flu incidence at 90% power.

B6. Endpoint Analyses

Primary Analysis

[figure not shown]
Question: Does this home-based self-test diagnostic tool and rapid treatment intervention lead to a large percentage of influenza-positive individuals initiating antiviral therapy within 48 hours of symptom onset?

Endpoint: Cumulative incidence of influenza virus infection

Measure of Association:
Cumulative Incidence (Attack Rate, Incidence Proportion)

$$\text{Cumulative Incidence} = \frac{\text{Number of participants that successfully initiate antiviral therapy within 48 hours of symptom onset (among participants who have a cough and self-test positive for influenza) during the October 2019-May 2020 influenza season}}{\text{Number of influenza-free participants at risk at } t_0 \text{ (baseline)}}$$

Relevant DAG

Exposure:

Exposed (Treatment) = Participants who develop cough and self-test positive
Unexposed (No treatment) = Participants who develop cough but self-test negative

Outcome:

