Success = Participant initiated on antiviral therapy within 48 hours of symptom onset
Failure = Participant is not initiated on antiviral therapy (**more than 48 hours** after symptom onset *or* participant **never** initiates antiviral therapy)

Table 1. Estimated secondary attack rates for planned 2019-2020 study aim on household transmission dynamics.

The study is being conducted in the Seattle, WA area over one influenza season. The goal is to enroll at least 250 (up to 1,000) households. Of these, 25% are estimated to have an individual in the household diagnosed with influenza based on estimates from previous household studies.^{23, 28-29}

A table for influenza attack rates by household size is provided below.

Household attack rate	Total households enrolled	Primary cases	Secondary cases (mean household size 5)	Secondary cases (mean household size 4)	Secondary cases (mean household size 3)
25%	250	63	45-96	34-72	23-48

20%	250	50	36-76	27-57	18-38
10%	250	25	18-38	14-29	9-19
Mean household size includes case.					
Secondary attack rate 18-38%, secondary cases presented as a range based on these high and low bounds.³⁰⁻³²					

Incidence Density

Using time-specific variables such as date of enrollment, weekly symptom diaries and questionnaires, Incidence Density (ID) will be calculated, defined with the following formula:

Incidence Density =

Number of participants that successfully initiate antiviral therapy within 48 hours of symptom onset (among participants who have a cough and self-test positive for influenza)

Total person-days

Model

The proportion of individuals that 1) test positive and 2) receive and initiate treatment within 48 hours of symptom onset using home-based self-test and delivery methods will be analyzed with a binomial regression GLMM with a log link. The outcome follows a binomial distribution, with the number of successes in a series of n independent Bernoulli trials, where each trial has probability of success p . Successes here are defined as an individual successfully initiated on antiviral therapy within 48 hours of symptom onset using home-based self-test to diagnose influenza and home delivery of antivirals. The model is defined below:

Incidence proportions of influenza will be presented in tables.

A formal statistical comparisons between study periods (control vs. intervention) will be performed using a Wald test of the hypothesis

$H_0: RR=1$

$H_a: RR \neq 1$

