The general form of the model (in matrix notation) is:

$$\mathbf{y} = \log\left(\frac{p}{1-p}\right) = \mathbf{X}\boldsymbol{\beta} + \mathbf{Z}\mathbf{u} + \boldsymbol{\epsilon}$$

Variable	Definition
\mathbf{y}	$N \times 1$ column vector, the outcome variable
\mathbf{X}	$N \times p$ matrix of the p predictor variables
$\boldsymbol{\beta}$	$p \times 1$ column vector of the fixed-effects regression coefficients (the β s)
\mathbf{Z}	$N \times q$ design matrix for the q random effects (the random complement to the fixed \mathbf{X})
\mathbf{u}	$q \times 1$ vector of the random effects (the random complement to the fixed $\boldsymbol{\beta}$)
$\boldsymbol{\epsilon}$	$N \times 1$ column vector of the residuals, that part of \mathbf{y} that is not explained by the model height

where each individual β value represents the change in log-odds of receiving and initiating treatment within 48 hours, that are associated with a particular demographic or clinical risk factor. A one-sided test with $\alpha = .05$ will be used. A table of the estimated Risk Ratios for a one unit increase in each covariate, given the other covariate values will be presented, along with the corresponding 95% confidence intervals, and p-values.

Data cleaning and analysis

All analyses will be performed in R version 3.6.1 using the package 'lme4.'

Secondary Analyses:

Question: How well does the self-test perform in comparison to the gold standard molecular test?

Sensitivity, specificity, PPV and NPV of the self-test will be calculated and compared to the gold standard molecular test. Table 2 (below) presents relevant formulas.

Table 2. Sensitivity, Specificity, PPV, and NPV of the Ellume Self-Test, SFS Household Intervention Study, 2019-2020 influenza season

Test Score	The Truth	
	Has Influenza	Does Not Have Influenza
Positive	True Positives (TP) a	False Positives (FP) b
Negative	False Negatives (FN) c	True Negatives (TN) d

$$\text{Sensitivity} = \frac{TP}{TP+FN} = \frac{a}{a+c} \quad \text{Specificity} = \frac{TN}{TN+FP} = \frac{d}{d+b}$$

$$\text{PPV} = \frac{TP}{TP+FP} = \frac{a}{a+b} \quad \text{NPV} = \frac{TN}{TN+FN} = \frac{d}{d+c}$$

Question: What is the association between influenza infection and: (1) influenza strain (by genetic sequencing) and (2) viral kinetics (maximum titer, duration viral RNA detection)?

Sensitivity analysis

Sensitivity analyses will be performed to explore the uniformity of any treatment effects found in the overall analysis.

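### SAP B6 names a log link but writes a logit model and then tabulates Risk Ratios; if the written equation is fitted, odds ratios would carry a risk-ratio label

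*SAP*

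**What the plan says.** Four statements in SAP B6, under Model, bear on the same regression:

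- **Link named.** Starting treatment within 48 hours "will be analyzed with a binomial regression GLMM with a log link", and the hypothesis set out for the Wald test is RR = 1.
- **Equation displayed.** The general form is log(p/(1−p)) = Xβ + Zu + ε. The outcome vector y is set equal to the logit, and ε is defined as a residual vector.
- **Meaning of β.** Each coefficient "represents the change in log-odds of receiving and initiating treatment within 48 hours" for a demographic or clinical factor.
- **Reporting.** "A table of the estimated Risk Ratios for a one unit increase in each covariate" is to be presented, with 95% confidence intervals and p-values.

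The software line names R 3.6.1 and lme4 but no link option.

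The protocol is consistent on this. Section III (Primary Outcome Measures) says of the primary proportion: "It will be calculated using binomial regression with log link". Section XI, on the covariate analysis, says "Binomial regression with log link will be used to calculate the relative risk of receiving and initiating treatment within 48 hours".

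**The concern.** The exponentiated coefficient of a log-link model is a risk ratio; that of a logit model is an odds ratio. The SAP names the first model, writes and interprets the second, and labels the output as if the first had been fitted. Two analysts could each follow the text and fill the same table with different quantities.

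The gap between the two ratios grows with the outcome proportion, and both documents hope for a high one. The protocol's primary hypothesis is that the approach "will result in a large percentage of drug eligible individuals diagnosed with influenza initiating antiviral therapy within 48 hours", and the SAP asks whether it will "lead to a large percentage of influenza-positive individuals initiating antiviral therapy within 48 hours of symptom onset". At stake are the sizes of the covariate associations and their confidence intervals.

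The residual term is a smaller error in the same equation. In a binomial model the random variation comes from the binomial distribution, and nothing is added to the linear predictor beyond Zu.

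**Working it through.** **The plan's own figure.** The only number given for the primary proportion is the 95% CI half-width in protocol Section XI. 250 × 0.25 = 62.5, rounded to 63; 1.96 × 0.5/√63 = 0.1235, which agrees with the stated 0.12. This calculation does not use the link function.

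**Relation between the two ratios.** With success proportions p0 (reference) and p1:

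- RR = p1/p0
- OR = [p1/(1−p1)] / [p0/(1−p0)] = RR × (1−p0)/(1−p1)

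If p1 > p0, the last factor exceeds 1 and OR > RR > 1. If p1 < p0, OR < RR < 1. If p1 = p0, both equal 1. A mislabelled ratio therefore keeps its direction, is right at the null, and otherwise lies further from 1.

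**Size when success is common.** The documents give no expected proportion, so these pairs are assumptions:

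| Assumed p1 v p0 | RR | OR |
|---|---|---|
| 90% v 80% | 0.90/0.80 = 1.13 | (0.90/0.10)/(0.80/0.20) = 9/4 = 2.25 |
| 84% v 70% | 0.84/0.70 = 1.20 | (0.84/0.16)/(0.70/0.30) = 5.25/2.33 = 2.25 |
| 80% v 60% | 0.80/0.60 = 1.33 | (0.80/0.20)/(0.60/0.40) = 4/1.5 = 2.67 |
| 60% v 50% | 0.60/0.50 = 1.20 | (0.60/0.40)/(0.50/0.50) = 1.50 |

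Fitting illustrative data with 70% v 84% success both ways gave exp(β) = 1.20 with a log link and 2.25 with a logit link. A ratio of 2.25 read as a risk ratio against an 80% reference would imply 0.80 × 2.25 = 180% success, which is impossible.

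**Size when success is rare.** The cumulative-incidence formula in SAP B6 divides by all influenza-free participants at baseline. With at most 63 successes in 250 households:

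- 5 members each: 63/1,250 = 5.0%
- 4 members each: 63/1,000 = 6.3%
- 3 members each: 63/750 = 8.4%

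At p0 = 5% and RR = 1.2, p1 = 6% and OR = (0.06/0.94)/(0.05/0.95) = 1.21. At p0 = 6.3% the OR is 1.22. Here the mislabelling would hardly matter.

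**Which statement is out of line.** The named link, the RR = 1 hypothesis, the risk-ratio table and both protocol sections point to a log link. The equation and the log-odds sentence point to a logit. Protocol version 3.1 (January 14, 2020) is also later than the SAP (last revised 10/8/19).

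**The case against.** The strongest defence is that most of the specification already says log link and risk ratio. The equation is offered only as a general form, and its list of definitions reads like generic mixed-model text. A sensible analyst would fit the named link, and the risk-ratio label would then be correct. This stands in part: mislabelling follows only if the displayed equation is fitted. It does not remove the contradiction. The logit appears in the equation and again in the prose on β, and nothing in the SAP says which takes precedence.

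A reader might infer that every covariate effect would be greatly overstated. The documents do not support that. Null effects are unchanged, direction is unchanged, and the size depends on a proportion that neither document states. The SAP is also unsettled on the denominator, and with its whole-cohort formula the two ratios nearly agree. On the other side, the protocol's denominator (drug eligible, self-test positive and laboratory-confirmed) and the SAP's own question concern people with influenza, among whom a high proportion is hoped for.

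A reader might also infer that the primary result is compromised. It is not. Protocol Section III defines the primary outcome as one count divided by another, and the relative risks by covariate are a further analysis in Section XI.

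**Conclusion.** SAP B6 contradicts itself on the link function and the meaning of its coefficients, and its equation contradicts protocol Sections III and XI. That much is certain from the text. The consequence is conditional: if the displayed logit is fitted, odds ratios would be reported as risk ratios. The discrepancy would be large if success is common (2.25 in place of 1.13 for an assumed 90% v 80%) and negligible at about 5-8%. The covariate ratios and their confidence intervals are exposed; the estimate of the primary proportion is not. The documents do not show that odds ratios will in fact be mislabelled, only that the SAP as written permits it. The correction should be made before analysis because it removes the ambiguity at almost no cost.

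**What to change.** In SAP B6, Model:

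1. Replace the equation with log(p) = Xβ + Zu and delete ε and its definition. Keep Zu, because the SAP specifies a mixed model; dropping it would be a change of model.
2. Replace the log-odds sentence with one that defines β as the change in log risk and exp(β) as the risk ratio, conditional on the random effects. B6 then matches protocol Sections III and XI.
3. Name a fallback in case the log-binomial model does not converge. A log link does not keep fitted probabilities below 1. With about 63 cases, an assumed 90% success leaves only about 63 × 0.10 = 6 failures, against six listed covariate types. One option is a logit model whose predictions are standardised to risk ratios, with the interval method stated.

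Keeping the logit and reporting odds ratios under that name would also be coherent, but it would depart from the protocol's relative risk.

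The cost is a wording change to the SAP and a little extra programming for the fallback. No data collection or sample size changes.

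### The SAP tests covariate effects one-sided at 0.05 without naming a direction, beside 95% confidence intervals and a two-sided alternative; two-sided 0.05 should be stated throughout

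*SAP*

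**What the plan says.** The Model part of SAP section B6 makes three statements about inference:

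- For study periods: "A formal statistical comparisons between study periods (control vs. intervention) will be performed using a Wald test of the hypothesis" RR = 1, with RR ≠ 1 as the alternative. That alternative is two-sided.
- For the regression coefficients, described as changes "that are associated with a particular demographic or clinical risk factor": "A one-sided test with" alpha = 0.05 is to be used. No direction is given for any coefficient.
- For the table of risk ratios by covariate: estimates are to be shown "along with the corresponding 95% confidence intervals, and p-values".

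Protocol section XI plans the same kind of covariate analysis. It names demographics (age, sex, race or ethnicity) and the type, severity and duration of symptoms, and states: "The RR, 95% confidence intervals and p-values will be reported". It does not say whether those p-values are one-sided or two-sided. Its primary objective is estimation: "We define precision in terms of the width of a 95% confidence interval".

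SAP section B5 gives a table of clusters per arm but states neither an alpha nor a number of sides.

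**The concern.** A one-sided test is fully specified only when its direction is stated. Here none is, and the covariates do not suggest one. Sex or age could be associated with starting treatment in time in either direction, and factors with several categories, such as race or ethnicity, have no single direction.

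A one-sided 0.05 test also uses a different cut-off from a 95% confidence interval. The planned table would show both for each risk ratio, so a row could be significant by its p-value and not by its interval, or the reverse. With no direction written down, nothing in the SAP prevents the side from being chosen after the estimate is seen. What is at stake is which factors are reported as associated with starting treatment within 48 hours.

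**Working it through.** **1. Which sidedness the plan's own figures use.** Inputs from SAP B5: ICC 0.29, cluster size 4, control rate 0.15, power 0.80 and 0.90. Alpha is not stated, so both versions were tried.

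Design effect = 1 + (4 − 1) × 0.29 = 1.87.

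Clusters per arm = (z_alpha + z_power)² × [p1(1 − p1) + p2(1 − p2)] / (p1 − p2)² × 1.87 / 4, rounded up, with p1 = 0.15.

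The columns are labelled as reductions, but the table is reproduced only when they are read as risk ratios (p2 = 0.15 × column value). For the first cell, p2 = 0.045, so the variance term is 0.1275 + 0.042975 = 0.170475 and the squared difference is 0.105² = 0.011025.

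- Two-sided 0.05: (1.960 + 0.842)² × 0.170475 / 0.011025 × 1.87 / 4 = 56.7, so 57. The SAP gives 57.
- One-sided 0.05: the same with 1.645 gives 44.7, so 45.

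| Power | SAP B5 | Two-sided 0.05 | One-sided 0.05 |
|---|---|---|---|
| 0.80 | 57 / 84 / 129 | 57 / 84 / 129 | 45 / 66 / 102 |
| 0.90 | 76 / 112 / 172 | 76 / 112 / 172 | 62 / 91 / 141 |

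All six cells match two-sided 0.05 and none matches one-sided 0.05. With the columns read as reductions, two-sided 0.05 matches only the 0.50 column (where the two readings coincide) and one-sided 0.05 matches nothing. Pooled variance with two-sided 0.05 comes within 2 clusters. A continuity correction does not match.

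The protocol's precision figure also uses the two-sided 95% multiplier: 1.96 × 0.5 / √63 = 0.123, stated as 0.12.

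**2. Where p-value and interval part.** One-sided 0.05 rejects at z = 1.645. A Wald 95% interval excludes 1 only beyond |z| = 1.960. With a fixed direction:

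- z from 1.645 to 1.960 in the tested direction (one-sided p from 0.05 down to 0.025): significant, but the interval includes 1. Probability under the null: 0.05 − 0.025 = 2.5%.
- z beyond 1.960 in the other direction: the interval excludes 1, but the one-sided p exceeds 0.975. Probability under the null: 2.5%.
- Everywhere else the two agree.

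**3. Type I error per test.**

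- Direction fixed in advance: 5%.
- Direction taken from the data, or the 1.645 cut-off applied to RR ≠ 1: 2 × 0.05 = 10%.
- Two-sided 0.05: 5%, and p < 0.05 exactly when the Wald 95% interval excludes 1.

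**The case against.** The strongest defence is that the SAP describes two different tests. RR ≠ 1 is written for the control-versus-intervention period contrast, while the one-sided sentence follows the covariate coefficients. A reader might infer that the SAP gives two contradictory rules for one test. The text does not establish that, because RR ≠ 1 is never stated for covariates. This part of the defence stands. What remains is the clash within the covariate table itself, where one-sided 0.05 p-values sit beside 95% intervals, and the SAP's failure to say which rule covers which test.

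The one-sided sentence might instead be meant for the period contrast, where the SAP does suggest a direction: B5 speaks of reducing influenza incidence, and section C expects 150 against 120 events per 1000. But those figures concern influenza incidence, whereas the model defines success as starting antiviral therapy within 48 hours. They supply no direction for the modelled risk ratio.

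It is also fair to say that a one-sided test with a direction set in advance and a matching interval would be coherent. That is true, but the SAP provides neither.

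Finally, the analysis at issue is a covariate table in a pilot, and neither document ties a study decision to it. That limits the consequences without making the rule usable as written.

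**Conclusion.** The one-sided sentence should be changed. It names no direction, does not match the 95% intervals reported for the same risk ratios, and is at odds with the sidedness used elsewhere in the plan.

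Three stronger conclusions might be drawn, and the documents support none of them:

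- *That p-values and intervals will generally disagree.* They disagree only in the two zones shown above, 2.5% + 2.5% = 5% of tests under the null.
- *That the true error rate is 10%.* This is the worst case. It applies if the side is chosen from the data or 1.645 is used for both tails. The SAP is silent on direction and does not say that it will follow the data.
- *That the primary result is compromised.* The protocol's primary estimate is a single proportion with a 95% interval. No test is involved, and it is unaffected.

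The size of the problem is therefore a cut-off of 1.645 instead of 1.960, and a type I error between 5% and 10% per test depending on a choice the SAP leaves open. The figures assume Wald tests and Wald intervals with a normal approximation. The inference that B5 is two-sided assumes that its columns are risk ratios and that the unpooled formula was used. One-sided 0.025 would give the same cluster numbers, but one-sided 0.05 would not.

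**What to change.** Replace the one-sided sentence in SAP B6, Model, with: *All tests, for the covariate effects and for any comparison of RR = 1, are two-sided at 0.05.* This agrees with the 95% intervals, the RR ≠ 1 alternative and the B5 calculation, and it settles which rule applies to which test. The B5 cluster counts do not change.

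The cost is one sentence and slightly fewer nominally significant covariates: an estimate must lie 1.960 / 1.645 = 1.19 times as far from the null, in standard errors, to be declared significant.

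If one-sided testing is really intended, the SAP should state the direction for each contrast and report a matching interval. For one-sided 0.05 that is a 90% two-sided interval or a one-sided 95% bound.

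### The jointly adjusted risk-ratio model for on-time treatment is specified inconsistently (log link in words, logit in the equation), and a joint log-link fit at about 63 cases would usually lie on the boundary, with no fallback named

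*SAP*

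**What the plan says.** Protocol section XI plans log-link binomial regression to obtain relative risks of on-time treatment by demographic and clinical factors, "including age, sex, race/ethnicity, symptom types, symptom severity, and duration of symptoms", with confidence intervals and p-values. SAP section B6, under Model, calls for a "binomial regression GLMM with a log link" and then promises: "A table of the estimated Risk Ratios for a one unit increase in each covariate, given the other covariate values will be presented".

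The matrix equation printed in the same SAP section has log(p/(1−p)) on the left. The text below it says that each coefficient "represents the change in log-odds of receiving and initiating treatment within 48 hours". That is a logit model.

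On size, the protocol states: "With 250 households participating and an attack rate of 25% we expect 63 individuals with confirmed influenza infection". The only precision statement is for one proportion: "This will give a 95% CI for the proportion initiating treatment of" ±0.12 or less. The SAP gives a wider enrolment range: "The goal is to enroll at least 250 (up to 1,000) households".

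Neither document states how the covariates are coded, how many parameters the model has, what the random effects are, what on-time proportion is expected, or what happens if the model does not converge.

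**The concern.** A log-link binomial model is valid only if every fitted probability is at most 1. When most people succeed and several covariates enter together, the likelihood tends to peak where some fitted probabilities equal 1. The usual normal theory fails at that edge, so Wald standard errors, intervals and p-values cannot be relied on, and ordinary software may not converge.

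If the analyst follows the printed equation instead, the constraint disappears. The exponentiated coefficients are then odds ratios, not the promised risk ratios, and with few late or untreated cases the fit can separate.

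Either way the analyst would have to choose the link, coding or estimator after seeing the data. The reported predictors of on-time treatment would then depend partly on those choices. The model appears under the SAP's Primary Analysis heading, so a reader may give its results more weight than they can bear.

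**Working it through.** **1. The plan's own figures.** 250 × 0.25 = 62.5, rounded to 63. The half-width is 1.96 × 0.5/√63 = 0.123, stated as 0.12. Both reproduce, but they size a single proportion and not a regression.

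**2. Parameters.** The coding is not given, so only a range can be stated.
- Smallest joint coding: intercept plus one term for each of six factors = 7.
- Fuller coding, as an assumption: intercept 1 + age 1 + sex 1 + race 6 (seven levels in SAP Table 1a) + symptom types 11 (distinct entries in the protocol's Symptom Table) + severity 1 + duration 1 = 22. Adding cough or categorical severity would raise this.

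**3. Failures.** The documents hope for a large share on time but give no number. Assuming 70–90%, failures number 63 × 0.30 = 18.9 down to 63 × 0.10 = 6.3. Per parameter that is 2.7 to 0.9 with 7 parameters, and 0.9 to 0.3 with 22.

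**4. How often the log-link maximum is on the boundary.** Datasets were simulated with no true covariate effects and assumed covariate distributions. The log-binomial likelihood was maximised subject to all linear predictors being ≤ 0. A fit counted as on the boundary if any fitted probability exceeded 0.9999. There were 200 datasets per setting at 25, 50 and 63 cases and 100 at 250 cases.

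| Model | Cases | 70% on time | 80% | 90% |
|---|---|---|---|---|
| 7 parameters | 25 | 99% | 100% | 100% |
| 7 parameters | 50 | 95% | 98% | 100% |
| 7 parameters | 63 | 93% | 97% | 100% |
| 22 parameters | 63 | 100% | 100% | 100% |
| 7 parameters | 250 | 11% | 37% | 82% |
| 22 parameters | 250 | 100% | 100% | 100% |
| Age alone | 63 | 7% | 19% | 45% |
| Sex alone | 63 | 0% | 1% | 4% |

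The 25 and 50 cases are the protocol's own figures for 10% and 20% household attack rates. The 250 cases are 1,000 × 0.25. At 63 cases the 22-parameter model averaged about 21 after empty columns were dropped. Repeat runs of the 7-parameter, 63-case setting ranged from 89% (at 70% on time) to 100% (at 90%). At 250 cases they ranged from about 11% to 83%. If only 50% were on time, the 63-case figures would be 59% with 7 parameters and 100% with 22.

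**5. The printed logit form.** At 63 cases and 70%, 80% and 90% on time, separation occurred in 97%, 99% and 100% of datasets with 22 parameters, and in 1%, 1% and 28% with 7. The scale also matters when success is common. For 90% versus 80% on time the risk ratio is 0.90/0.80 = 1.13, while the odds ratio is (0.90/0.10)/(0.80/0.20) = 2.25.

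**6. Other denominators.** If later cases in a treated household are kept as failures (86 to 159 people), the 22-parameter log-link fit is still on the boundary in 90–100%. If everyone enrolled is the denominator, as in the SAP's cumulative-incidence formula (750 to 1,000 people, about 5–7% success), the boundary rate is 0%. Separation or empty cells still occur in 70–80% of those datasets (40 per setting). That denominator is not the one in the protocol's primary outcome.

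**7. Random effects.** The 63 are primary cases, one per affected household. If a household intercept is meant, it would have almost no replication among them.

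**The case against.** The documents do not force the worst case. The protocol's wording can be read as one factor at a time, where most fits are interior. The SAP's phrase about the other covariate values points to joint fitting, but the SAP lists no covariates there and calls its equation a general form. The boundary argument does not apply to the printed logit equation. Enrolment could reach 1,000 households, where a 7-parameter log-link fit is often interior. All of this stands, and it limits how firmly the point can be put.

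Four stronger readings are tempting and are not supported:
- **That the model has 22 parameters.** This is a reconstruction from a descriptive table and a symptom list. The documents fit anything from about 7 upward.
- **That there will be 6 to 19 failures.** This rests on an assumed 70–90%. The protocol bars further study drug once one household member is treated, so later cases kept in the denominator would add failures.
- **That analysts would be forced to drop covariates.** A robust-variance Poisson model avoids the boundary without dropping any. Overfitting would remain, but that is a milder problem.
- **That the primary result is compromised.** The primary outcome is a single proportion sized by its interval width, and it does not depend on this model.

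The objection does not remove the central point. If the log link in the text and the mutual adjustment in the SAP are both followed at the protocol's case count, the fit usually fails even with the fewest parameters, and nothing says what to do then.

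**Conclusion.** The concern holds in a limited form. The link is contradictory, and the coding and fallback are missing. Under a joint log-link reading at 63 cases with 70–90% on time, about 89–100% of simulated datasets have their maximum on the boundary with only 7 parameters, so the promised intervals and p-values would usually not be valid. At about 250 cases this falls to about 11–83% with 7 parameters. Under the logit reading the output is not a risk ratio, and separation ranges from 1–28% (7 parameters) to 97–100% (22 parameters).

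These figures rest on an assumed success range, assumed covariate distributions and no true effects. Simulation error is up to about 5 percentage points in the 250-case rows. These are supplementary predictor analyses in a single-arm feasibility pilot, so this should be fixed before analysis but is not a fatal flaw.

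**What to change.** In protocol section XI and SAP section B6 (Model), replace both the log-link binomial GLMM and the logit equation with one risk-ratio model: Poisson regression with log link and robust variance clustered by household. Remove the random-effects term and the log-odds definition, and amend the software statement to match.

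Report risk ratios one factor at a time for a short prespecified list: age, sex, race/ethnicity collapsed to stated categories, one Day 0 severity score, and symptom duration with its time of measurement stated. Show individual symptom types as counts of on-time and not on-time cases. Give the counts beside each risk ratio as well, because the robust variance is uninformative in a category where everyone succeeded. Delete the clause about the other covariate values, or allow only one small adjusted model with its terms named in advance. Label all these risk ratios exploratory.

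Single-factor reporting alone is not enough if the log-binomial model is kept, since age by itself was on the boundary in 7–45% of datasets.

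The cost is a change of wording in the two documents. What is given up is a fully mutually adjusted set of risk ratios, which about 63 cases cannot support. Robust intervals will also be approximate where late or untreated cases are few, which is a further reason for the exploratory label.
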